2.0 Justification Document

Click the Add button to upload document(s) to support justification, including any data collection forms and/or information sheets/letters to be provided to research subjects:

Name	Version	Orig. Author	Orig. Created	Last Modified
Appendix A	0.01	[name]	4/29/2016 9:09 PM	4/29/2016 9:09 PM
Decision Tree	0.01	[name]	3/31/2016 8:44 PM	3/31/2016 8:44 PM
Information Sheet/Consent	0.03	[name]	3/30/2016 5:27 PM	4/4/2016 11:47 AM
Simulation Slides	0.01	[name]	4/29/2016 9:08 PM	4/29/2016 9:08 PM

Pro00054122: A simulation study to assess whether informing physicians of out-of-pocket cost to patients and malpractice history influences ordering. - [name]

[View: Protocol - Study Protocol](#)

Study Protocol

1.0 * Select the category that applies to your research study protocol:

Investigator generated protocol/research plan

2.0 Protocol document, grant application, or research protocol

* Click the Add button to upload these document(s). (**Note: Do NOT upload consent or any other documents here.**)

Name	Version	Orig. Author	Orig. Created	Last Modified
[name] Total Protocol	0.02	[name]	3/30/2016 5:35 PM	4/1/2016 7:39 PM

3.0 Protocol Summary Information (as applicable):

3.1 Study Protocol Version: 1 Dated: 3/30/2016

3.2 Sponsor Assigned Amendment Number: Dated:

Pro00054122: A simulation study to assess whether informing physicians of out-of-pocket cost to patients and malpractice history influences ordering. - [name]

View: Study Populations - Study Subjects

Study Subjects

1.0 * Estimated Local Enrollment Goal

Enter the anticipated number of subjects to be enrolled at local site:
75

2.0 Estimated Study-Wide Enrollment Goal

Enter the anticipated number of subjects to be enrolled at all sites:
200

3.0 * Briefly describe the setting in which the research will be conducted.

The research will be available online at an NIH website, which can be accessed by study participants at their choice of location and electronic device.

4.0 * Participant Remuneration (Payment/Academic Credit)

Will subject(s) receive remuneration?
 Yes No

5.0 * Will prospective participants be vulnerable to coercion or undue influence?

Yes No

If yes, briefly describe additional safeguards included in the protocol to protect the rights and welfare of participants likely to be vulnerable.

6.0 * Identify targeted subject population(s) involved in this research study (Note: The purpose of this question is to determine equitable selection of subjects and to identify vulnerable populations.)

Select all that apply:

Adults (18+)

Males

Females

Pregnant Women

Human Fetuses or Neonates

Minorities

Children (<18 years of age)

Prisoners

Comatose persons

Cognitively Impaired persons

- Terminally Ill persons
- Employees of the principal investigator's institution**
- Students enrolled at the principal investigator's institution
- Non-English speaking persons
- Socially/Economically disadvantaged persons
- Caregivers
- Elderly/Aged persons
- Institutionalized Individuals

7.0 * Study Population

Briefly describe the study population? (e.g. healthy volunteers, adults with Type II Diabetes, children with Asthma):
Emergency Department providers: Doctors, Nurse Practitioners, and Physician Assistants

8.0 * Describe the selection criteria (inclusion/exclusion criteria):

a. Inclusion Criteria: Regardless of assignment to group, basic inclusion criteria include:

- 1) Licensed physician or physician trainee;
- 2) Board certified, board eligible or trainee in Emergency Medicine; and
- 3) Serve as an attending physician or trainee affiliated with the Greenville Health System.

b. Exclusion Criteria: All others not meeting inclusion criteria are excluded.

9.0 * Describe recruitment procedures, including how subjects will be contacted, by whom, and how eligibility will be determined.

Participants will be contacted by the Academic Vice Chair, [name] MD, through their work email address with information about the study and a link to the website where the simulation may be completed.

Eligibility will be determined by an employee roster provided by [name], the business operations coordinator of the Emergency Trauma Center.

Pro00054122: A simulation study to assess whether informing physicians of out-of-pocket cost to patients and malpractice history influences ordering. - [name] View: Funding and Sponsorship - Study Funding Information

Study Funding Information

1.0 * Primary Funding Source (Active or Pending)

Select primary (active or pending) funding sources for this study:
Internal Funding

Pro00054122: A simulation study to assess whether informing physicians of out-of-pocket cost to patients and malpractice history influences ordering. - [name] View: Funding and Sponsorship - Study Sponsorship

Study Sponsorship

1.0 Sponsor(s)

Click the Add button and select the sponsor(s)

Name

There are no items to display

2.0 Other Sponsor(s)

If sponsor(s) is/are not in the above list above, enter name(s) here:

GHS and Clemson University

3.0 External Identifier (if applicable):

(e.g. agency/sponsor assigned numbers)

4.0 Internal Identifier (if applicable):

(e.g. proposal or award Number)

Pro00054122: A simulation study to assess whether informing physicians of out-of-pocket cost to patients and malpractice history influences ordering. - [name]

View: Funding and Sponsorship - Study Costs

Study Costs

Study Associated costs funded by:

1.0 Drug(s):

Sponsor

If OTHER, specify:

2.0 Device(s):

N/A

If OTHER, specify:

3.0 Supplies:

N/A

If OTHER, specify:

4.0 Laboratory Fees:

N/A

If OTHER, specify:

5.0 Hospital Fees:

N/A

If OTHER, specify:

6.0 Physician Fees:

Sponsor

If Other, specify:

7.0 **Other:**
N/A

If OTHER, specify:

Pro00054122: A simulation study to assess whether informing physicians of out-of-pocket cost to patients and malpractice history influences ordering. - [name]

View: Checklist - Application Checklist

Application Checklist

1.0 **Will the following be involved in the research study?**

Select all that apply

- Waiver of the Requirement to Obtain Written and Signed Consent from Subjects**
- Medical Record/Chart Review
- Use of survey, questionnaire, focus group/interview questions
- Interviews/Group Discussion
- This research study is being conducted by other investigators in other countries
- Videotaping, audiotaping, filming or photographing research subjects
- Data from the statewide Health Sciences South Carolina (HSSC) Clinical Data Warehouse ?

Pro00054122: A simulation study to assess whether informing physicians of out-of-pocket cost to patients and malpractice history influences ordering. - [name]

View: Other Study Specifics - Clinical Trials

Clinical Trials

1.0 *** What is the phase of the clinical trial?**

This study does not involve a clinical trial

2.0 **If OTHER, describe:**

Pro00054122: A simulation study to assess whether informing physicians of out-of-pocket cost to patients and malpractice history influences ordering. - [name]

View: Other Study Specifics - Study Procedures

Study Procedures

(Blood draw, Imaging, Lab Tests, Physical Exam, Medical History)

1.0 *** Briefly describe the procedures to be performed solely as part of this research study.**

N/A

2.0 *** Briefly describe the procedures being performed already for diagnostic or treatment purposes (standard of care).**

N/A

Pro00054122: A simulation study to assess whether informing physicians of out-of-pocket cost to patients and malpractice history influences ordering. - [name] View: Consent Process - Waiver of Written or Signed Consent

Consent Process - Waiver of Written or Signed Consent

If a waiver of written signed informed consent is requested, please provide justification.

1.0 * Check one of the following and explain your choice:
 The research presents no more than minimal risk and involves no procedures for which written consent is normally required outside the research context.

*** Explain:**
 Simulated cases, presentation of evidence based medicine, and educational opportunities are not only part of medical culture, but are expected to take place at medical centers offering residency training programs in the United States.

Reviewing medical decision making, cost data, and discussing malpractice are topics that are well within the scope of a normal work day for a medical provider.

For these reasons, our research team asserts that there is no more risk to participants of our research study than they would encounter on any given day working in an emergency department.

2.0 * If signed documentation is waived, will the subjects be provided with a written statement/explanation regarding the research?
 Yes No

If YES, attach a copy of written statement.

Name	Version	Orig. Author	Orig. Created	Last Modified
Information Sheet	0.01	[name]	4/4/2016 11:49 AM	4/4/2016 11:49 AM

If NO, explain below why a written statement is not necessary or appropriate.

Pro00054122: A simulation study to assess whether informing physicians of out-of-pocket cost to patients and malpractice history influences ordering. - [name] View: Privacy - Privacy and Confidentiality

Privacy and Confidentiality

1.0 * Describe the procedures and safeguards that will be implemented to protect the privacy and confidentiality of the participants' data. Include details, as applicable to the study, such as: privacy of interview site, procedures for coding/de-identifying data, provisions to avoid public identification/embarrassment of participants; persons with access to private identifiable data, etc.

Storage, Access, and Transmission:

Storage:

1. On the GHS server, or on a GHS approved laptop that has been secured by the GHS Information Services department
2. GHS SharePoint Rad Team page owned and operated by [name], approved by GHS Information Services.
http://share.ghs.org/SiteDirectory/eduserVICES/radteam/default.aspx
3. GHS RedCap web application, username [name]

Access:

[name], the owner of these projects, controls the GHS SharePoint Rad Team page and Redcap application page. Access will be granted to individuals who have documented approval from GHS to view the data in question.

Transmission:

Data with protected health information may be transmitted to individuals who have approval from GHS to view the data in question by means of:

1. GHS outlook secure email
2. Sharing access through the aforementioned GHS SharePoint Rad Team page
3. Approving access to the GHS Redcap application
4. Sending files securely through the GHS Redcap application

Authorization expiration: upon contract end date

[name]

2.0 * Where will study records and data collected at this site be stored

Select all that apply:

Password protected network storage

If OTHER, describe:

If information will be stored on an end-user/portable device, describe the security on the end-user/portable device that will be used to prevent unauthorized access to the data in the event the device is lost or stolen:

3.0 * Will the study use a National Institutes of Health (NIH) Certificate of Confidentiality?

Yes No

If YES, what is the NIH Certificate of Confidentiality status?

Pro00054122: A simulation study to assess whether informing physicians of out-of-pocket cost to patients and malpractice history influences ordering. - [name] View: Privacy - Protected Health Information (PHI) for Research

Protected Health Information (PHI) for Research

Protected Health Information (PHI) is defined as individually identifiable health information transmitted or maintained in any form (electronic means, paper, or oral communication) that relates to the past, present, or future physical or mental health or conditions of an individual.

Covered Entity - A health plan, a health care clearinghouse, or a health care provider who transmits health information in electronic form.

1.0 * To determine if this research study is using/disclosing PHI, select any of the following 18 elements that your study will require access to, as defined by the Health Insurance Portability and Accountability Act (HIPAA), as identifiers. If none of these 18 identifiers will be used/disclosed, then select the final option.

Electronic mail addresses

If the study requires access to any of the 18 identifiers but will not be linked to PHI, please select those that are applicable to the left. On the next screen, you will be able to select "Study where health information is not linked to identifiers".

Pro00054122: A simulation study to assess whether informing physicians of out-of-pocket cost to patients and malpractice history influences ordering. - [name] View: Privacy - Access to Protected Health Information (PHI) for Research

Access to Protected Health Information (PHI) for Research

1.0 Indicate the sources of health information to be used

Select all that apply:

There are no items to display

If OTHER, indicate any other source(s) of health information to be collected/used:

2.0 How will PHI be accessed for the research study? (Check all those that apply)

Study where health information is not linked to identifiers

Pro00054122: A simulation study to assess whether informing physicians of out-of-pocket cost to patients and malpractice history influences View: Privacy - Use of De-Identification to Access Protected Health Information (PHI)

**ordering. - [name]**

Use of De-Identification to Access Protected Health Information (PHI)

1.0 The Privacy Rule permits covered entities, depending on IRB approval, to use and disclose data that have been de-identified without obtaining an authorization. The Principal Investigator must receive the data from the covered entity in a de-identified format. A covered entity may de-identify PHI in one of two ways. The first method requires the removal of every one of 18 identifiers enumerated at section 164.514(b)(2) of the Privacy Rule. Data that are stripped of these 18 identifiers are regarded as de-identified. The second way to de-identify PHI is to have a qualified statistician determine, using generally accepted statistical and scientific principles and methods, that the risk is very small that the information could be used, alone or in combination with other reasonably available information, by the anticipated recipient to identify the subject of the information.

The Privacy Rule permits a covered entity to assign to, and retain with, the health information a code or other means of record identification if that code is not derived from or related to the information about the individual and could not be translated to identify the individual. The covered entity may not use or disclose the code or other means of record identification for any other purpose and may not disclose its method of re-identifying the information.

*** Will you be receiving de-identified information from a covered entity for the purpose of this project?**

Yes No

Pro00054122: A simulation study to assess whether informing physicians of out-of-pocket cost to patients and malpractice history influences ordering. - [name] View: Institution Impacted Services - Institution Impacted Services

Institution Impacted Services

Prior to IRB approval, the investigator for this research study must obtain authorization from any services impacted by the research. Many studies require significant levels of support or collaboration from staff and departments in order to fully execute the proposed study.

1.0 * Will the research study use any property, facilities, equipment, or services of the institution?

Yes No

Pro00054122: A simulation study to assess whether informing physicians of out-of-pocket cost to patients and malpractice history influences ordering. - [name]

View: General Comments

General Comments

1.0 Add any additional comments to assist in the review of this research study.

2.0 Add any miscellaneous documents that do not fit in other sections of the study application.

Click Add to upload document(s)

Name	Version	Orig. Author	Orig. Created	Last Modified
CV of [name]	0.01	[name]	4/11/2016 10:11 AM	4/11/2016 10:11 AM
CV of [name]	0.01	[name]	4/2/2016 9:16 AM	4/2/2016 9:16 AM
CV of [name]	0.01	[name]	4/4/2016 2:06 PM	4/4/2016 2:06 PM
CV of [name]	0.01	[name]	4/2/2016 9:16 AM	4/2/2016 9:16 AM
Signature Page 1	0.01	[name]	4/29/2016 9:06 PM	4/29/2016 9:06 PM
Signature Page 2	0.01	[name]	4/29/2016 9:06 PM	4/29/2016 9:06 PM

Pro00054122: A simulation study to assess whether informing physicians of out-of-pocket cost to patients and malpractice history influences ordering. - [name] View: SF - Final Page

Final Page

This is the end of the application. Click the Finish button to close the forms and return to the Application workspace. Click Edit Application Forms in the Application workspace to return to the forms at any time.

NOTE: Clicking Finish does not submit the application for review; this activity can only be executed in the Application workspace by the PI.

**Title: Effect of clinical decision rules, patient cost and malpractice information on clinician brain CT image ordering: A randomized controlled trial**

**Statistical Analysis:**

Data were recorded in our intervention server, housed at the National Institutes of Health, in a Microsoft Excel spreadsheet. The data were downloaded and analyzed using SAS, ver. 9.4 (Cary, NC). In our study, because clinicians' ordering image vs. not ordering image was the main comparison of interest, CT brain modalities (with or without contrast) were grouped together and compared with the no imaging order group. To compare the clinicians' change in image ordering, McNemar test was employed and a multiple comparison adjustment was performed using Bonferroni correction. For the comparison of the demographic or other professional characteristics among different clinician groups, Chi-square test was employed to compare the proportions of categorical variables; if more than 20% of the cells had sample size less than 5, Fisher Exact test was applied instead. Analysis of Variance (ANOVA) test was used to compare the mean (standard deviation) of continuous variables.

A sample size of 155 will achieve 80% power to detect a difference in the proportion of selecting CT imaging if 30% of clinicians choose CT order in the absence of evidence and change to no imaging order when the evidence is presented and 15% of clinicians choose no imaging order in the absence of evidence and changed to CT order when the evidence is presented.

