Date: Wednesday, November 16, 2016 5:00:11 PM

Print Close

Pro00054122 : A simulation study to assess whether informing physicians of out-of-pocket cost to patients and malpractice history influences ordering. - [name]

View: Study Identification - Identification

VIEW000072

Study Identification Information

This is the first step in your Human Research Application. You will automatically be guided to the appropriate forms needed to complete your submissions.

1.0 * Full Title:

Enter the full study title

Physician use of cost and malpractice information in medical imaging decision making: A deeper look into the factors influencing physician ordering of head CT scans in patients with minor head trauma.

2.0 * Short Title:

Enter a short descriptive title for this study (65 characters maximum):

A simulation study to assess whether informing physicians of out-of-pocket cost to patients and malpractice history influences ordering.

3.0 * Briefly describe the scientific or scholarly rationale:

(i.e. purpose of research)

The purpose of the proposed research is to determine whether the introduction of information regarding litigation history and out-of-pocket cost to patients will influence head CT ordering behavior by Emergency Physicians in a simulated clinical encounter. This research is important as the literature suggests that financial motives and fear of malpractice are two of the most influential factors when Physicians order head CTs. Results from this study will advise future studies and the potential development of targeted clinical decision support for Emergency Physicians. Optimal medical image study ordering will enhance patient safety and potentially save the health system millions of dollars annually.

4.0 * Brief Study Summary

Non-scientific description of the research study, using 3 to 10 sentences:

Statements such as "see protocol" are not acceptable.

Note: Text entered in the Brief Study Summary field will be used to describe your study at www.SCresearch.org, an online directory designed to facilitate recruitment, if inclusion on this site is indicated later in the application.

There is a huge push to cut back on medical spending, lead by the changes in how Medicare reimburses hospitals for patient care. We aim to explore the effects of informing physicians about out-of-pocket patient costs of head CT scans, and educating physicians on the the history of malpractice cases involving failure to order head CT scans.

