Measure #2 – study ordered when exposed to the Canadian Head CT decision rule: Participants will be provided with information on the sensitivity, specificity, and validation studies that have supported this decision support rule. They will then be given the same imaging options to choose from as the baseline measure – two variations of CT scan, and no imaging.

Measure #3 – study ordering when exposed to malpractice data: Participants will be provided the history of all the cases where physicians were sued for not ordering a head CT scan for patients. With this information, they will be given the option to change which imaging order they would choose in the same case.

Measure #4 – study ordering when exposed to cost information: Participants will be provided information on the cost of a CT order to the patient taken from billing data from the parent institution. They will then be given the three imaging options, and asked what they would choose given

the new information.

Measure #5 – demographic information: We will be collecting basic demographic information on the participants including status (e.g. attending or trainee, military or civilian), age (scaled response not specific age), gender, and years of practice (scaled response from attending physicians).

All data will be collected during the experiment with no planned follow-up activity or engagement with the research participants. The study data, de-identified, will be secured by password in the PI's computer.

Rationale for Exempt criteria:

Simulated cases, presentation of evidence based medicine, and educational opportunities are not only part of medical culture, but are expected to take place at medical centers offering residency training programs in the United States.

Reviewing medical decision making, cost data, and discussing malpractice are topics that are well within the scope of a normal work day for a medical provider.

For these reasons, our research team asserts that there is no more risk to participants of our research study than they would encounter on any given day working in an emergency department.

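### Holm's step-down procedure would keep the same familywise error bound as the SAP's Bonferroni correction and gain power when two or more comparisons have real effects

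*SAP*

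**What the plan says.** The SAP (Statistical Analysis) first reduces the outcome to any CT against none: "CT brain modalities (with or without contrast) were grouped together and compared with the no imaging order group". It then states the test, "To compare the clinicians' change in image ordering, McNemar test was employed", and the multiplicity rule, "a multiple comparison adjustment was performed using Bonferroni correction". It describes no step-down, ordered or gatekeeping procedure. It does not give the number of comparisons, the alpha level or the sidedness.

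The sample size statement in the same section reads "A sample size of 155 will achieve 80% power". It assumes that 30% of clinicians switch from CT to no imaging and 15% switch the other way.

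The documents allow more than one family of comparisons:

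- **Two**, if the family follows the Protocol's rationale (Study Identification, item 3.0), which concerns "the introduction of information regarding litigation history and out-of-pocket cost to patients".
- **Three**, if it follows the SAP title: "Effect of clinical decision rules, patient cost and malpractice information on clinician brain CT image ordering".
- **Six**, if all pairs of the four ordering decisions in the Protocol's exemption justification (baseline, decision rule, malpractice, cost) are tested: 4 × 3 / 2 = 6.

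The tests are dependent. The same clinicians answer one case repeatedly; at the malpractice step, for example, "they will be given the option to change which imaging order they would choose in the same case".

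**The concern.** Single-step Bonferroni holds every one of k tests to alpha/k, however strong the other results are. Holm orders the p-values, tests the smallest at alpha/k, the next at alpha/(k−1) and so on, and stops at the first failure. Its first threshold equals Bonferroni's and the later ones are larger. It therefore cannot lose a rejection that Bonferroni makes, and it has the same familywise bound without any assumption about how the tests are correlated. That last property matters here because every test uses the same people and the same case.

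Power is at stake, not validity. The trial has none to spare if its sample size took no account of the planned adjustment. A clinician-information effect that is real could then be declared non-significant when an equally rigorous rule would have declared it.

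**Working it through.** **Inputs.** From the SAP: N = 155, power 80%, p10 = 0.30 (CT to none), p01 = 0.15 (none to CT), McNemar test. Assumed: two-sided alpha 0.05; k = 3 comparisons as the main case, with k = 2 and 6 as the range; 30%/15% for each real effect and 22.5%/22.5% for each null one; all 155 clinicians in each test.

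**Step 1: reproduce the plan's figure.** Normal approximation for McNemar:

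n = [z(1−α/2)·√(p10+p01) + z(power)·√(p10+p01−(p10−p01)²)]² / (p10−p01)²

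- √0.45 = 0.6708; √(0.45 − 0.0225) = √0.4275 = 0.6538
- n = (1.960 × 0.6708 + 0.8416 × 0.6538)² / 0.0225 = 154.6, rounded up to 155

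The plan's figure is reproduced at an unadjusted two-sided 0.05 (power at 155 is 80.1%). The variants tried do not give it: 122 one-sided, 162 with continuity correction, 150 with unpooled variance, 152 conditional on discordant pairs.

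**Step 2: power per comparison under Bonferroni at N = 155.**

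Power = Φ{[(p10−p01)·√N − z(1−α/2k)·√0.45] / √0.4275}

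For k = 3: (0.15 × 12.450 − 2.394 × 0.6708) / 0.6538 = 0.400, and Φ(0.400) = 65.5%.

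| k | Level per test | Power at 155 | N for 80% |
|---|---|---|---|
| 1 | 0.05 | 80.1% | 155 |
| 2 | 0.025 | 71.1% | 188 |
| 3 | 0.0167 | 65.5% | 207 |
| 6 | 0.0083 | 55.9% | 240 |

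**Step 3: Bonferroni against Holm by simulation.** Uncorrected McNemar chi-square, 200,000 trials per scenario, run with independent tests and with tests sharing one baseline (assumed baseline CT rate 60%). A normal-approximation run (400,000 trials) took the correlation between test statistics to 0.8. Figures are average power per real comparison, k = 3.

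| Real effects | Bonferroni | Holm, independent | Holm, shared baseline | Holm, correlation 0.8 |
|---|---|---|---|---|
| Three | 66% | 75.7% | 74.3% | 72.3% |
| Two | 66% | 69.9% | 69.3% | 68.5% |
| One | 65–66% | 65.7% | 65.6% | 65.6% |

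- **All real effects found (independent tests):** with three real, 28.3% under Bonferroni and 50.7% under Holm; with two real, 43.0% and 51.5%. With a shared baseline and three real: 39.7% and 58.9%.
- **At least one rejection among the three tests:** identical for the two methods. Holm's first step is Bonferroni's test of the smallest p-value. With independent tests it is 96.0%, 88.4% and about 67% for three, two and one real effects.
- **Familywise error (independent tests), Bonferroni then Holm:** 4.7% and 4.7% under the global null; 3.1% and 4.2% with one real effect; 1.6% and 3.7% with two. Across all family sizes and both dependence settings, Holm's maximum was 4.96%.
- **Other family sizes:** k = 2 with both real, 72% to 77–78%; k = 6 with three real, 56% to 59–60%.
- **Dominance:** Holm rejected every hypothesis that Bonferroni rejected, in every simulated trial.

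**The case against.** The case for leaving the SAP alone is reasonable.

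**Bonferroni is not wrong.** It is standard, and it also controls familywise error under any dependence. This stands; the point is about efficiency only.

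**It may be too late.** The analysis text is in the past tense: "The data were downloaded and analyzed using SAS". Moving to a more liberal rejection rule after seeing results carries little confirmatory weight. This also stands, although the sample size sentence is in the future tense, so the timing is not certain. It limits how a switch may be presented, and does not make Holm inferior.

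**The gain assumes equal effects.** The SAP gives 30%/15% once and does not say that each kind of information has that effect. With one comparison at 30%/15% and two weaker ones at an assumed 25%/17.5% (independent tests), the main effect goes from about 66% to 68% and the others from 16% to 21%. With the other two at an assumed 24%/20%, the main effect gains less than one point.

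**All 155 may not enter every test.** The SAP title calls the study randomized and the Protocol's inclusion criteria refer to group assignment, while the exemption justification describes one sequence taken by everyone. With an assumed 75 clinicians per test, power goes from about 33% to 37.5% with three real effects and from about 33% to 35% with two.

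The last two objections shrink the gain but cannot reverse it. Independent tests are also the least plausible setting here, so the shared-baseline and correlated columns are the better guide.

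**Conclusion.** The concern holds as an efficiency improvement. For any alpha and any number of comparisons, Holm rejects at least what Bonferroni rejects at the same familywise bound; that does not rest on the unstated values.

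The size of the gain does rest on assumptions: three comparisons, two-sided 0.05, 155 clinicians per test and 30%/15% for each real effect. On those, power per real comparison rises by about 6 to 10 points with three real effects and about 3 to 4 with two, and is essentially unchanged with one. Unequal effects or fewer clinicians per test make the gain smaller.

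Holm does not repair the sample size. The 155 was sized without the adjustment, and that mismatch is larger than the difference between the two procedures.

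**What to change.** In the SAP's Statistical Analysis section, replace the Bonferroni phrase with: Holm step-down Bonferroni across the stated family of McNemar comparisons, two-sided familywise alpha 0.05. List the comparisons in that family, since the adjustment cannot be reproduced without them, and report Holm-adjusted p-values.

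If results have already been seen, keep Bonferroni as the stated rule and show Holm beside it, labelled post hoc.

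The cost is one phrase and a short list, with no new data. Holm has no simple matching simultaneous confidence intervals. If intervals are wanted, report Bonferroni ones and note that an interval may include zero for a comparison that Holm rejects.
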